3.4 Location and duration of procedures

All study visits will take place on an outpatient basis in the UPMC Shadyside Radiation Oncology Department. However, it is possible that a subject may be an inpatient at the time of diagnosis. The duration of study visits will vary dependent on the procedures to be completed during that study time-point. We expect for visits to last between 1-4 hours.

3.5 Timeline of study procedures

Once eligible by screening, stereotactic radiosurgery will take place, 1-7 days later, there will be a surgical removal of the tumor. Monitoring will take place 10-14 days after surgery, every 3 months for the first year and every 4 months thereafter.

3.6 Research Activities

3.6.1 Pretreatment Evaluation

The following tests/procedures will be performed in order to ascertain subject eligibility within 28 days prior to registration unless otherwise specified.

- Complete physical evaluation with a performance status, vital signs, height, and weight, and a complete medical history.
- CT (computed tomography) scan of the brain

- MRI (Magnetic Resonance Imaging) Scan of the brain
- For women of child bearing potential, a urine pregnancy test will be done. If this come back positive or questionable, a serum pregnancy test will be completed by taking a small sample (about 1 teaspoonful) of blood. Pregnant women, or women who are currently breast-feeding an infant, will not be allowed to take part in this study.
- Pretreatment blood sample for research bank if patient agrees.

In addition to the procedures listed above, the following Quality of Life questionnaire will be done for research purposes:

- FACT – BR (FACT – BRAIN) - This assessment will take approximately 5 (five) minutes to complete.

3.6.2 Evaluation during treatment

Administration of stereotactic radio surgery:

Patients will receive a single fraction pre-operative SRS radiation dose. The dose will be determined depending on diameter of the tumor as follows: 24 Gy, 18 Gy, and 15 Gy for tumors < 21 mm, 21-30 mm, and 31-40 mm in maximum diameter respectively.

Dose	Diameter
15 Gy	31-40 mm
18 Gy	21-30 mm
24 Gy	< 21mm

Tumor tissue collection only if participant agrees and there is leftover from clinical collection.

Blood sample collection pre and post SRS treatment (within 24 hours)

Complete physical evaluation with a performance status, vital signs, height, and weight, and a complete medical history

3.7 Surgical removal

One to seven days after the single SRS, patient will then be prepared for surgical removal of the tumor that was designated by surgeon as part of normal standard of care for dominant brain metastasis. Only the symptomatic tumor will be removed surgically. Surgery will be performed at Shadyside Hospital.

3.8 Follow-up procedures

Standard care procedures will be performed and assessed 10-14 days post-surgery. These include:

- Complete physical evaluation with a performance status (a measure of how well you carry on daily activities), vital signs (blood pressure, temperature, heart rate, respiration rate), height, and weight, and a complete medical history. MRI (magnetic resonance imaging).
- Scan of the brain will be performed every 3 months after your surgical procedure. If additional brain metastases are detected on one of your follow up scans, then they will be treated as per standard of care, likely using either additional SRS or whole brain radiation.

In addition, patient will be asked to complete a health-related quality of life assessment at each visit. The assessment is for research purposes and will take approximately 5 (five) minutes to complete.

2.5 SUBJECT SELECTION AND ELIGIBILITY

4.1 Selection of subjects

Enrollment is defined as the first day of protocol therapy.

Patients enrolled in this study must have a measurable brain metastasis which is defined as lesions that can be accurately measured in at least one dimension: [longest diameter to be recorded] on the MRI scan. Patients will have no more than 4 distinct lesions within the brain. The target lesion must measure at least 15mm in at least one dimension and no more than 40mm in any dimension.

4.2. Screening and sample size

50 patients will be screened with an expectation that 24 patients will proceed to study protocol. Patients will not be excluded based upon gender nor ethnicity. This study will be limited to adults, in whom stereotactic radiosurgery is a common treatment modality used in the management of brain metastases. Brain metastases are less frequent in children and when they do occur are often represented by histologies with an increased sensitivity to radiotherapy and would have drastic differences in clinical outcome. Research with children under the age of 18 is conducted at Children's Hospital of UPMC.

4.2.2 Justification of sample size/accrual rate

No more than 24 evaluable patients will be treated in the trial. This study of 24 patients will have 80% power to detect a difference in postulated local tumor control of 85% to a known inference local tumor control set at 60% to be excluded, using a 1-sided test with Type I error rate of 0.05 for 6, 12, and 24 months. The sample size was estimated using a non-inferior power analysis for inference of a single proportion compared to a known proportion. Also, an attrition rate of 20% was included into the estimated sample size. Based on previous efforts in recruiting patients at the University of Pittsburgh Cancer Institute, it is anticipated that at least 5 patients per year will be enrolled in the protocol and the accrual will be completed within 5 years. An evaluable patient is defined as one who completes a single fractions of preoperative SRS followed by surgical resection of appropriate brain metastases. Patients who are not evaluable will be replaced.

4.3 Identification and initiation of contact with study participants

Potential research subjects are first identified by their neurosurgeon ([name]). These patients will be deemed as candidates for surgical resection of their brain metastasis, either because of regional mass effect (i.e. pressure on other brain structures) or neurologic symptoms/signs related to the tumor (e.g. weakness, visual disturbance, gait dysfunction, seizures, speech disorder). Once a potential subject has been set up for surgical resection of a brain metastasis by [name] or [name], they will then be referred to radiation oncology for discussion of the clinical trial and potential up front SRS. "Cold-calling" will not be used to recruit subjects. "Finder's fees" for referring a potential subject for participation in a research study are prohibited.

Physicians and other health care professionals in the area are aware of active studies at the Department of Radiation Oncology at UPMC by means of various publications including the

World Wide Web. Such publication and Web listings are not advertisements for specific studies. Rather, they are public listings of trials available.

Once a subject is identified as a potential participant in a research study as indicated above, he/she is screened for eligibility. No identifiable information (e.g. name, diagnosis, treatment, etc.) will be released until the subject has given written authorization. No research-related procedures (including review of the subject's medical records) will be performed until the subject has provided written informed consent. The consent process will be carried out as a joint effort among the subject's physicians, the study coordinators, and a physician who is listed as an investigator on the study.

4.4 Inclusion criteria

Each subject must meet all of the following inclusion criteria to be enrolled in the study:

- a. Male or female patients \geq 18 years of age
- b. A life expectancy of at least 12 weeks with a Karnofsky performance status of at least 50 (Appendix I)
- c. Patient has no contraindications to MRI scanning with intravenous contrast.
- d. MRI scan consistent with brain metastasis as per radiology report.
- e. The target lesion must measure at least 15 mm in at least one dimension, and no more than 4 cm in any dimension.
- f. Patients must have an extra-cranial primary tumor diagnosis.
- g. Patients will have no more than 4 distinct lesions within the brain. At least 1 lesion has been recommended for surgical removal based on size, symptomology, or regional mass effect on the brain.
- h. The additional lesions will each be treated with stereotactic radiosurgery.
- i. Patients with a documented symptomatic lesion size smaller than 3cm requiring clinical surgical resection
- j. Must be aware of the neoplastic nature of his/her disease and willingly provide written, informed consent after being informed of the procedure to be followed, the experimental nature of the therapy, alternatives, potential benefits, side-effects, risks and discomforts.
- k. Signed consent

4.5.1 Exclusion criteria

Subjects meeting any one of the following exclusion criteria are not to be enrolled in the study:

- a. Primary tumor histology of lymphoma, leukemia, multiple myeloma or germ cell tumor.
- b. Moribund status or status epilepticus.
- c. Supratentorial mass effect with greater than 5 mm of midline shift or hydrocephalus.
- d. Infratentorial mass effect with fourth ventricle effacement or hydrocephalus.
- e. More than four additional diagnosed brain metastases.
- f. Contraindication to general anesthesia.
- g. Adjacent tumor location to optic apparatus or brainstem, precluding achievement of meaningful dose with SRS.
- h. Primary brain tumor.
- i. Contraindication to MRI scans or intravenous contrast.

j. Pregnant and breast-feeding females.

4.5.2 Specific criteria to exclude pregnant females and feta/neonatal exposure

For all females who are not at least one year post-menopausal or who have not undergone a surgical sterilization procedure, a urine pregnancy test will be done. If this is positive or questionable a serum pregnancy test will be done. The results of the pregnancy test must be negative in order for the patient to participate in this study.

Women who are pregnant or breastfeeding are excluded from participation in this study. All females of childbearing potential must have a serum pregnancy test within 14 days of the radiation. The results of the pregnancy test must be negative for the patient to participate in this study.

Subjects will be informed by the study staff that is extremely important that they not become pregnant or father a baby while participating in this study, and that avoiding sexual activity is the only certain method of preventing pregnancy. However, if a subject chooses to be sexually active, he or she must agree to use an appropriate "double barrier" method of birth control starting from the subject's participation in the screening process and continuing until two weeks following the subject's participation in the study. Birth control methods can include intrauterine device (IUD), contraceptive sponge and spermicide, in addition to male use of a condom, or the female should be using prescribed birth control implant. Subjects will be instructed to notify the study doctor of their birth control method prior to the start of the study, and also if they plan to change their birth control method.

Subjects that choose to be sexually active must be made aware that even with the use of birth control measures, pregnancy could still result. Subjects will be informed that if they become pregnant or impregnate a woman while taking part in this study, they must immediately notify one of the doctors listed on the consent form.

The information listed above will be relayed to applicable subjects by the study staff. It will also be listed in the consent form, a copy of which will be provided to the patients for them to take home.

5.0 TREATMENT EVALUATION, ADMINISTRATION, AND MODIFICATION

5.1 Tissue constraints

Treatment shall be delivered via linear accelerator (LINAC) commissioned and equipped to deliver stereotactic radiosurgery. Normal tissues and sensitive critical structures (e.g. spinal cord, brainstem, optic nerves, optic chiasm, and pituitary) shall be contoured and the dose to these organs limited. Normal tissue constraints are outlined below.

Normal Tissue Constraints:

Organ Maximum Dose in 1 Fractions

Brain V12 <5-10 cc Dose/Volume

Spinal Cord <13 Gy

Brainstem <12.5 Gy

Optic Nerves <12 Gy

Optic Chiasm <12 Gy

Pituitary <20 Gy

Cochlea <14 Gy Dose/Volume

Normal Tissue Constraints	
Organ	Maximum Dose in 1 Fraction
Brain V12	<5-10 cc Dose / Volume
Spinal Cord	< 13 Gy
Brainstem	<12.5 Gy
Optic Nerves	<12 Gy
Optic Chiasm	<12 Gy
Pituitary	<20 Gy
Cochlea	<14 Gy Dose / Volume

5.2 Dose Specification, Homogeneity Considerations & Plan Evaluation

The treatment plan used shall be based on the assessment of the dose-volume histogram (DVH) with attention to coverage of the planning tumor volume (PTV) and critical normal structures.

The prescription dose is the isodose cloud that encompasses at least 80% of the PTV.

No more than 20% of any PTV shall receive doses >110% of its prescribed dose.

No more than 2% of any PTV shall receive <93% of its prescribed dose.

No more than 5% of any normal tissue shall receive doses in excess of 110% of the primary PTV dose.

5.3 Follow-up procedures

Patients will be seen in follow-up 10-14 days post treatment then every 3 months for 12 months, then every 4 months up until 3 years, with the following evaluations:

- Complete physical evaluation with a performance status, vital signs, height, and weight, and a complete medical history
- MRI scans at 3 months post-treatment and every 3 months for 12 months, then every 4 months up until 3 years for assessment of response to therapy and

6.0 STUDY EVALUATION

6.1 Pre-research screening

After signing consent form, participant will undergo the following screening tests and/or procedures (some may not have to be repeated if they were recently performed as part of standard of care):

- Complete physical evaluation with a performance status (a measure of how well you carry on daily activities), vital signs (blood pressure, temperature, heart rate, respiration rate), height, and weight, and a complete medical history.
- CT (computed tomography) Scan of the brain (an imaging test that takes many x-rays from different angles to form images of the brain).
- MRI (Magnetic Resonance Imaging) Scan of the brain (an imaging test that uses no radiation, but rather a magnetic field to create high detailed images of the brain)
- For women of who are not at least one year post-menopausal or who have not undergone a surgical sterilization procedure, a urine pregnancy test will be done. If this comes back positive or questionable, a serum pregnancy test will be completed by taking a small sample (about 1 teaspoonful) of blood from a vein in the arm for a pregnancy test. Pregnant women, or women who are currently breast-feeding an infant, will not be allowed to take part in this study.
- A health-related quality of life assessment for research purposes. This assessment will take approximately 5 (five) minutes to complete.

6.2 Ending subject's participation in the study

A subject's participation in the study will be halted if any one of the following would occur:

- Pregnancy test proves to be positive.
- Disease status becomes worse.
- Develop side effects from treatment.
- Physician feels that this preoperative SRS is no longer in your best interest.
- Patient is not compliant with the study.

6.3 Treatment schema

Parameter	Pre-Study	SRS	Within 24 hrs post SRS	Surgical resection 1-7 days post SRS	10-14 days post surgery	Q3 months for 12 months, then q4 months to 3 years
History	X	X		X	X	X
Physical exam	X	X		X	X	X
Vital Signs	X	X			X	X
Performance Status	X	X			X	X
MRI	X					X
CT Scan for treatment planning	X					
Serum or Urine Pregnancy Test for WOCBP	X					
FACT - Brain assessment	X				X	X
Blood sample for research *		X	X			

6.4. Tumor response on CT (RECIST)

Measurable Disease Response: CTEP's RECIST guidelines will be followed. A quick reference to the RECIST guidelines can be downloaded at the following URL:
<http://ctep.info.nih.gov/Policies/WordDocs/RCSTF.PH2TEMPF.doc>.

6.5 Post-surgery procedures

Patients will be seen in follow-up 10-14 days post treatment then every 3 months for 12 months, then every 4 months up until 3 years, with the following evaluations:

- Complete physical evaluation with a performance status, vital signs, height, and weight, and a complete medical history
- MRI scans at 3 months post-treatment and every 3 months for 12 months, then every 4 months up until 3 years for assessment of response to therapy and monitoring.
- Administration of Fact-Brain questionnaire at each follow-up visit/scan.

7.0 STATISTICAL CONSIDERATIONS

7.1 Study objectives and design

The primary objective of this study is to determine the efficacy of giving pre-operative radiosurgery to patients pending resection of a brain metastasis.

The secondary objectives of this study include:

1. To evaluate overall survival (OS)
2. To evaluate distant intracranial failure associated with this therapy.
3. To evaluate the Health Related Quality of Life (HRQL) associated with this therapy.

This clinical trial is planned as a prospective single-arm phase II study.

7.2 Sample size and accrual rate

No more than 24 evaluable patients will be treated in the trial. This study of 24 patients will have 80% power to detect a difference in postulated local tumor control of 85% to a known inference local tumor control set at 60% to be excluded, using a 1-sided test with Type I error rate of 0.05 for 6, 12, and 24 months. The sample size was estimated using a non-inferior power analysis for inference of a single proportion compared to a known proportion. Also, an attrition rate of 20% was included into the estimated sample size. Based on previous efforts in recruiting patients at the University of Pittsburgh Cancer Institute, it is anticipated that at least 5 patients per year will be enrolled in the protocol and the accrual will be completed within 5 years. An evaluable patient is defined as one who completes a single fractions of preoperative SRS followed by surgical resection of appropriate brain metastases. Patients who are not evaluable will be replaced.

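### The stated 80% power at one-sided 0.05 is not delivered by the single-proportion test used for sizing once the plan's own 20% attrition is applied, and the analysis section names no test against 60% that would deliver it

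*Combined protocol and SAP*

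**What the plan says.** Section 7.2, repeated word for word in 4.2.2, sets the size of the trial. It caps enrolment ("No more than 24 evaluable patients will be treated in the trial") and attaches the power to that number: "This study of 24 patients will have 80% power" when true local control is 85%, against a "known inference local tumor control set at 60% to be excluded". The error rate is set by "using a 1-sided test with Type I error rate of 0.05 for 6, 12, and 24 months". The method is described as a "non-inferior power analysis for inference of a single proportion compared to a known proportion"; whether that is exact or approximate is not said, and no success cut-off is given. The attrition allowance sits inside the 24: "an attrition rate of 20% was included into the estimated sample size".

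The same sections define an evaluable patient as one who has had the single radiosurgery fraction and the resection. Only non-evaluable patients are replaced. No follow-up is required to count as evaluable.

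Section 7.4.1 plans to analyse local control at 6, 12 and 24 months with Kaplan-Meier curves and a log-rank test. It names no comparator and does not mention the 60% rate.

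**The concern.** If 20% attrition is already in the 24, the sizing calculation expects about 19 patients with a known outcome. A binomial test is coarse at that number: moving the cut-off by one patient changes both size and power a great deal. An approximation that looks right on paper may then correspond to no cut-off that gives both 0.05 and 80%.

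This matters because the protocol gives no cut-off. A result of 15 of 19 controlled would exclude 60% under one common test and fail to do so under another, and nothing in the plan decides which applies. Losses after surgery are foreseeable, since section 4.4 asks only for a life expectancy of 12 weeks and a Karnofsky score of 50, while the outcome is read at up to 24 months. Such patients remain evaluable and are not replaced.

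**Working it through.** **Inputs (sections 7.2 and 4.2.2).** Null rate 0.60, alternative 0.85, one-sided 0.05 (z = 1.645), power 80% (z = 0.842), 24 patients, 20% attrition included. Each calculation below is for one time point.

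**1. Reproducing the plan's figure.**
- Normal approximation: n = [(1.645 × √(0.6 × 0.4) + 0.842 × √(0.85 × 0.15)) / 0.25]² = 19.58, rounded up to 20. Approximate power is 80.9% at n = 20 and 78.7% at n = 19.
- Arcsine approximation: n = (1.645 + 0.842)² / [4 × (arcsin√0.85 − arcsin√0.60)²] = 18.76, rounded up to 19. Then 19 / 0.8 = 23.75, rounded up to 24.

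So 24 patients with 80% power and 20% attrition is a reproducible figure, with about 19 or 20 analysed.

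**2. Patients with a known outcome.** 24 × 0.8 = 19.2, so 19.

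**3. Exact binomial results.** Size is P(X ≥ c) at 0.60; power is P(X ≥ c) at 0.85.

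| n | Cut-off c | Size | Power |
|---|---|---|---|
| 19 | 16 (holds 0.05) | 2.3% | 68.4% |
| 19 | 15 (uncorrected normal) | 7.0% | 85.6% |
| 20 | 17 (holds 0.05) | 1.6% | 64.8% |
| 20 | 16 (uncorrected normal) | 5.1% | 83.0% |
| 21 | 17 (holds 0.05) | 3.7% | 80.3% |
| 22 | 18 (holds 0.05) | 2.7% | 77.4% |
| 23 | 19 (holds 0.05) | 1.9% | 74.4% |
| 24 | 19 (holds 0.05) | 4.0% | 86.1% |

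At 19 or 20 patients no cut-off gives size at or below 0.05 together with power of at least 80%. Power is saw-toothed in n: among these sizes a test that holds 0.05 reaches 80% only at 21 and at 24. The breach at n = 20 is marginal (5.1%); at n = 19 it is not (7.0%).

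**4. Tests that keep censored patients.** Section 7.4.1 points to time-to-event methods, so these were simulated. Assumptions, not taken from the documents: exponential local failure, independent exponential dropout reaching 20% by the time point, all 24 patients analysed, 40,000 runs per scenario.

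| Test against 60% | Size | Power at 85% |
|---|---|---|
| One-sample log-rank | about 3.7% | about 80-81% |
| Kaplan-Meier, log-log scale | about 3.4% | about 78% |
| Kaplan-Meier, plain Wald | about 7% | not relevant, as size is not held |

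The choice of test decides whether the stated pair is met.

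**The case against.** The strongest reply is that the plan names no exact binomial test, so 68.4% is not the power of anything it specifies. Kaplan-Meier and log-rank methods keep patients lost to follow-up as censored observations and do not reduce 24 to 19. This stands in part. A reader might infer that either the error rate or the power must be misstated whatever the analysis. The documents do not support that: under the assumptions above, a one-sample log-rank test on all 24 holds 0.05 with power of about 80%. But section 7.4.1 does not specify that test. A log-rank test with no comparator has nothing to compare in a single-arm trial, and the only test with stated error rates is the single-proportion one.

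A reader might also infer that the attrition was added wrongly, as 20 × 1.2 = 24 instead of 20 / 0.8 = 25. The documents do not show this. They give no pre-attrition number, and the arcsine route reaches 24 with correct division by 0.8. There is no ground for changing the stated 20%.

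Third, 24 evaluable patients could be read as 24 with a known outcome. Exact power is then 86.1%, above the claim. The definition of evaluable does not secure this, and the attrition sentence would then have no role, so 19 is the better-supported reading; the text is nevertheless ambiguous.

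Finally, a mid-p test would accept 15 of 19 (mid-p 0.046), and a continuity-corrected normal test would require 16, as the exact test does. The 7.0% applies to the uncorrected normal cut-off only.

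**Conclusion.** The point holds in a limited form. The 80% is a fair product of a standard approximation, not an arithmetic slip. The single-proportion test that the plan was sized on does not deliver 80% power with 0.05 held at the 19 patients its own attrition leaves: power is 68.4% at size 2.3%, or 85.6% at a true size of 7.0%. With all 24 assessable the power is 86.1%, which is also not the stated figure.

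The binomial figures rest on complete-case analysis of 19 or 24 patients at one time point. The time-to-event figures rest on exponential failure and on 20% independent dropout. The documents give no expected rate of death or loss by 6, 12 or 24 months for this population, so actual losses could differ from 20%, particularly at the later time points.

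**What to change.** In 7.2, 4.2.2 and 7.4.1, name one decision test against 60% and give that test's own size and power. Either of two routes would do:

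- **Exact one-sided binomial test.** Success is at least 19 of 24 if all are assessable (size 4.0%, power 86%), and at least 16 of 19 at 20% attrition (size 2.3%, power 68%). State the cut-off for the intermediate numbers too.
- **One-sample log-rank test, or Kaplan-Meier estimate tested on the log-log scale.** All 24 patients are analysed and censored patients are kept. Report simulated size and power at the dropout expected for each time point, with the assumptions.

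Do not use an uncorrected normal or plain Wald cut-off, since both can exceed 0.05 at this size. State how many patients are expected to be assessable at each time point. Leave the 20% attrition figure as it is, and add the pre-attrition number and the formula used.

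The cost is a few sentences and, for the second route, a short simulation. No patients are added. The stated power may become less favourable, notably 68% if the exact test is chosen and attrition is as planned.

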1.3 Pre-operative SRS

For patients who require surgical removal of a brain metastasis, we hypothesize a more sensible strategy to improve LC may be the delivery of pre-operative SRS followed by immediate tumor resection. Pre-operative target delineation is likely to be more accurate and result in fewer marginal misses. Furthermore, this treatment package could be completed more expeditiously by eliminating the prolonged interval from surgery to SRS. In our experience, this interval was approximately 5 weeks. In addition, the same MRI scan could be used for SRS and surgical resection; resulting in cost savings for patients who otherwise would receive two separate MRI scans for treatment. Finally, pre-operative SRS may facilitate better resection margins by the delivery of dose in the radiation penumbra surrounding the tumor. An early study of pre-operative SRS on brain metastases by Stuart Burri et al., 2010 demonstrated actuarial LC of 97.7%, 84.6%, and 64.0% at six, twelve, and twenty four months, respectively [23]. More recently according to the interim analysis from a phase 1 study of pre-operative SRS for brain metastases by the University of Alabama, pre-operative SRS appears safe with low rates of wound complications or acute grade toxicity along with target volume reduction of 39% [24]. We therefore propose a phase II clinical trial to further investigate the efficacy of this novel approach.

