7.4.1 Analysis of the Primary Endpoints

Local control rates for 6 months, 12 months, and 24 months will be analyzed with Kaplan-Meier Survival Curves and the Log-Rank Test.

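### The 80% power stated for 24 months rests on 85% local control, a rate that the protocol's own cited series supports at 12 months but not at 24 months

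*Combined protocol and SAP*

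**What the plan says.** Section 7.2 sets the size of the trial: "No more than 24 evaluable patients will be treated in the trial". It continues: "This study of 24 patients will have 80% power to detect a difference in postulated local tumor control of 85" per cent. The benchmark that the trial is meant to rule out is 60%. A single specification then covers all three times: "using a 1-sided test with Type I error rate of 0.05 for 6, 12, and 24 months". The method is described as a "non-inferior power analysis for inference of a single proportion compared to a known proportion", and the section adds that "an attrition rate of 20% was included into the estimated sample size". Section 4.2.2 carries the same text.

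Section 7.4.1 makes all three times part of the primary analysis: "Local control rates for 6 months, 12 months, and 24 months will be analyzed with Kaplan-Meier Survival Curves and the Log-Rank Test". It states no success rule and does not single out one time.

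The background gives one set of local-control results for radiosurgery before resection. Section 1.3 says an early study "demonstrated actuarial LC of 97.7%, 84.6%, and 64.0% at six, twelve, and twenty four months, respectively". The other pre-operative study mentioned there is described by safety and target volume reduction, with no local control rate.

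**The concern.** One postulated rate and one rate to be excluded serve three times that are 18 months apart. The cited series falls by 97.7 − 64.0 = 33.7 points between 6 and 24 months. On a Kaplan-Meier curve, a constant 85% at 6, 12 and 24 months would mean no local failures at all between 6 and 24 months. The 85% is close to the cited 12-month figure (84.6%). At 24 months it is 85 − 64.0 = 21 points above the cited figure, which itself lies only 4 points above the 60% to be excluded.

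What is at stake is how the 24-month result will be read. Someone who takes section 7.2 at its word would treat failure to exclude 60% at 24 months as a negative result from a comparison with 80% power. If control resembles the cited series, that outcome is expected nearly every time and says little about the treatment.

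**Working it through.** **Inputs.** From section 7.2: n = 24, rate to be excluded p0 = 0.60, postulated rate p1 = 0.85, one-sided α = 0.05, power 80%, attrition 20%. From section 1.3: 0.977, 0.846 and 0.640 at 6, 12 and 24 months.

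**Step 1: the plan's own figure.** Normal approximation for one proportion against a fixed value:

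n = [(z₀.₉₅ √(p0(1−p0)) + z₀.₈₀ √(p1(1−p1))) / (p1 − p0)]²

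= [(1.645 × √0.24 + 0.842 × √0.1275) / 0.25]² = [(0.806 + 0.301) / 0.25]² = 19.6, so 20.

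Adding 20% gives 20 × 1.2 = 24 (dividing by 0.8 gives 25). The stated size reproduces.

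**Step 2: exact test with 24 assessable.** With X ~ Binomial(24, 0.60), the smallest critical value with P(X ≥ r) ≤ 0.05 is r = 19, with size 0.040. Power is P(X ≥ 19) at the true rate:

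| True local control | Source | Power, n = 24 |
|---|---|---|
| 97.7% | cited, 6 months | above 99.9% |
| 85% | postulated | 86.1% |
| 84.6% | cited, 12 months | 84.7% |
| 80% | assumed | 65.6% |
| 75% | assumed | 42.2% |
| 70% | assumed | 22.9% |
| 64.0% | cited, 24 months | 8.7% |

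The mismatch is confined to 24 months. The assumed rows show that it does not depend on 64.0% being exact.

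**Step 3: other methods and attrition, at 64.0%.** Normal approximation, n = 24:

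Φ{[(0.64 − 0.60)√24 − 1.645√0.24] / √(0.64 × 0.36)} = Φ{(0.196 − 0.806) / 0.48} = Φ(−1.27) = 10.2%.

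The arcsine version gives 10.7%. With 20 assessable the exact test needs 17 or more (size 0.016) and has 3.7% power. With 19 it needs 16 or more (size 0.023) and has 4.9%. The normal approximation gives 9.6% and 9.4% respectively. A simulated Kaplan-Meier version (n = 24, exponential times, one-sided log-log bound) gave about 7% to 9%, assuming no deaths or a median survival of 18 or 12 months. Overall the range is roughly 4% to 11%.

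**Step 4: size needed for 80% power at 64.0% against 60%.** [(0.806 + 0.842 × 0.48) / 0.04]² = [(0.806 + 0.404) / 0.04]² ≈ 915 patients.

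**Step 5: the 12-month statement after attrition.** At 84.6% the exact test has 84.7% power with 24 assessable but 62.8% with 20. The normal approximation with 20 gives about 79%. The gap arises because 16 of 20 has size 0.051, just over 0.05, so the exact test must move to 17.

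**The case against.** The strongest reply is that power is conditional on the rate assumed. Given 85% against 60%, the stated size is right, and the 9% answers a different question. That stands. A reader might infer an arithmetic error in section 7.2, and there is none. The defect is an assumption without support at one of the three times.

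Nor do the documents support saying that the protocol refutes its own 24-month assumption. The 64.0% is a background estimate from one early study, given without sample size, confidence interval or number at risk. A sponsor may expect to do better, but then a reason is needed, and none is stated. The postoperative results in section 1.2 do not supply one: the institutional series shows 76% at both 6 months and 1 year, which is below 85%, stops at 1 year and concerns a different treatment sequence.

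A reader might also infer that an effective treatment would be reported as failing. That goes too far. A true 64% is barely above the rate to be excluded, and a trial of 24 patients is not designed to separate the two. In addition, no success rule in the plan depends on 24 months; section 7.4.1 lists only curves and a test. Low 24-month power is also partly a product of holding the benchmark at 60% for all three times.

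Finally, moving the power statement to 12 months is not enough by itself, because step 5 shows that it depends on how many patients are assessable and on the test used.

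**Conclusion.** The concern holds as an unsupported design assumption that should be fixed. The 85% is supported at 12 months and exceeded at 6 months by the only relevant figures in the protocol, but not at 24 months. At the cited 64.0%, the 24-month comparison has about 9% power, with the range given in step 3, against the 80% stated. A true rate of 80%, 16 points above the cited result, would still leave power at about 66% with all 24 assessable.

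The headline figure assumes a one-sided test of a single proportion against 60% with all 24 patients assessable at 24 months, and takes the cited estimate at face value. The conclusion is that failure to exclude 60% at 24 months would be uninformative. It is not that the treatment would be wrongly condemned, that the sample size is miscalculated, or that the 6-month and 12-month comparisons are undermined when all 24 are assessable.

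**What to change.** In sections 7.2 and 4.2.2:

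- Attach the 85% against 60% power statement to 12 months. State the test and the number assessable that it assumes, since power at 84.6% ranges from 62.8% to 84.7% across the cases in step 5.
- Remove the 24-month power statement, or restate it as about 9% at the cited 64.0%.

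In section 7.4.1, report 24-month local control as a Kaplan-Meier estimate with a 95% confidence interval, and make no claim to exclude 60%. For scale, 15 of 24 controlled with no censoring is 62.5%, with an exact interval of 41% to 81%.

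The cost is a change of wording and a less favourable stated figure at 24 months. No patients, visits or procedures are added.
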